4.6 Handling of Missing Data

By definition, all subjects in the PP population will have sufficient data required to determine primary endpoints. In instances where some (but not all) of the data is missing, two situations are possible: 1) some data are not available but the data that is available indicates for certain the patient is a failure, and 2) the data that is available indicates a possible cure and nothing indicates a failure, but without complete data it is not possible to determine for certain it is indeed a cure. Thus, a patient with situation 1) will be considered evaluable, while a patient with situation 2) will be non-evaluable and thus not included in the PP population. Any patients with all data missing will also be non-evaluable.

For subjects who are not eligible for inclusion in the PP populations but who are eligible for inclusion in the mITT subject populations, all missing data will be imputed as worst-case scenario outcome (e.g. failure).

If adverse event start dates are missing or incomplete, the following rules will apply for determining if an event is to be considered treatment emergent. If start date is completely missing, start date will be set as same day as start of treatment and assumed to be at a time following subject's first dose. If start date is incomplete, the date closest to start of treatment will be assumed, without compromising the incomplete data available for the start date.

If study medication start dates are missing or incomplete, the following rules will apply for determining inclusion in the Safety population. If the start date is completely missing and there is no documentation indicating that the patient used study medication, the date will be left as missing and the patient will be excluded from the Safety population. If the start date is completely missing or incomplete and there *is* documentation that indicates the patient used study medication, the date will be imputed to the earliest date and time post-randomization that is consistent with the partial data, and the patient will be included in the Safety population.

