4.7 Efficacy Analyses

4.7.1 Primary Efficacy Analysis

The primary efficacy endpoint is the cure rate at the test-of-cure visit (Visit 2). Definitions of cure for each of the three infection studies are provided in [Section 4.3](#).

Subjects in all studies will be categorized as cure or failure for the mITT analyses, and as cure, failure or non-evaluable for the PP analysis. The number and percentage of subjects in each treatment group in each of these categories will be reported. Separate statistical analyses will be performed for each of the three infection studies. All treatment comparisons will be based on two-tailed 0.05 significance level hypothesis tests and 95% confidence intervals for the difference in proportion of successes in each treatment. The primary comparison of treatment groups for each study will be performed using a continuity corrected Chi-squared test and Wald continuity corrected confidence intervals. It is anticipated that in some treatment groups in one or more of the infection studies, there may not be sufficient expected cell counts for the Chi-squared test and confidence intervals based on the normal approximation to be

accurate. Therefore, if all expected cell counts are not at least 5, Fisher's Exact test and confidence intervals using the method of Chan and Zhang (1999) will be used.

The primary efficacy analysis for each of the three infection studies will be performed using the mITT population with worst case scenario imputation for missing data. Supportive analyses will also be conducted using the PP population.

Efficacy analysis will not be done for the ITT population, as subjects in the BV and Mixed studies who do not have a gram stain ≥ 4 , or subjects in the VVC and Mixed studies who do not have a positive yeast culture, are not evaluated for efficacy. These subjects do not return for Visit 2; rather, they have the Limited Termination visit for safety evaluations only.

BV Study: The primary statistical objective of the BV infection study is to demonstrate the superiority of BV Gel to Placebo Gel in the treatment of BV. The assessment of superiority will be performed by conducting a continuity corrected Chi-squared test for a difference in the proportion of BV cure between the two treatments. Also, a 95% two-sided confidence interval for the difference in proportion of BV cure between the two treatments will be constructed.

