4.7.2 Secondary Efficacy Analyses

Secondary efficacy endpoints are listed in [Section 4.3](#). These endpoints include variables that are categorical (including binary variables), ordinal (such as rating scores), or time to event variables (such as time to resolution of symptoms). The analysis of the secondary endpoints will be performed using the mITT population with worst case scenario imputation for missing data, with supportive analyses conducted using the PP population.

For the secondary endpoints that are categorical or ordinal with four or fewer levels (including binary outcome variables), the analysis will include the proportion of subjects with each criteria or each score, at baseline and endstudy. The comparison of treatment groups will be performed using Chi-squared tests if all expected cell counts are at least 5, and Fisher's Exact test otherwise. For binary outcomes, (clinical outcome, mycological outcome, and eradication [or persistence] of individual fungal species) 95% two-sided confidence intervals for the difference in proportions will also be constructed using the continuity corrected Wald intervals when Chi-square tests are appropriate, or the method of Chan and Zhang (1999) otherwise.

Secondary endpoints that are ordinal data with more than four levels, such as Nugent score, the median score at baseline, endstudy, and the change from baseline will be computed, in addition to the proportion of subjects at each level. Treatment comparisons will be performed using the Wilcoxon Rank Sum test.

The secondary endpoint of time to resolution of symptoms will be analyzed in each infection study by arm using log-rank tests to compare arms within each study and Kaplan-Meier plots. Kaplan-Meier estimates of the quartiles for time to resolution will be computed, along with 95% confidence intervals. Censoring times for the Kaplan-Meier estimates will be based on the date of last contact or visit 3 (whichever is earliest) if symptoms never resolved or the patient was an early withdrawal and status is unknown.

The analysis of eradication (persistence) of individual fungal species will be conducted in subgroups of subjects defined by fungal species present at baseline (for the VVC and Mixed Infection studies).

In addition, for each study a summary will be made of subjects classified as:

- Persistent Infection – no cure at Visit 2 or Visit 3
- Persistent Cure – cure at Visit 2 and Visit 3
- Late Cure – no cure at Visit 2 but cure at Visit 3

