- Recurrence – cure at Visit 2 but no cure at Visit 3

A descriptive analysis of the primary endpoint (cure rate) for BV subjects will be performed to assess the impact of loss of potency of the BV gel over time. The proportion of patients achieving a cure will be computed among cohorts of patients completing Visit 2 during each month the study was underway. These proportions will be tabulated by month for the BV Gel arms of the BV study and the mixed infection study. In addition, a plot of the proportions by month will be presented.

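### Imputing failure for a missing visit puts subjects in the wrong category of the Visit 2 to Visit 3 cure-status summary, notably Late Cure

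*SAP*

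**What the plan says.** **The summary.** Section 4.7.2 adds, for each infection study, a four-way classification: Persistent Infection, Persistent Cure, Late Cure ("no cure at Visit 2 but cure at Visit 3") and Recurrence ("cure at Visit 2 but no cure at Visit 3"). The list in Section 14.2 runs it on mITT (Table 14.2.21.1) and on PP (Table 14.2.21.2).

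**Missing data.** Section 4.6 says of the PP population: "Any patients with all data missing will also be non-evaluable". Its imputation rule covers a defined group: "For subjects who are not eligible for inclusion in the PP populations but who are eligible for inclusion in the mITT subject populations". For them, "all missing data will be imputed as worst-case scenario outcome (e.g. failure". Section 4.7.2 has a broader sentence: "The analysis of the secondary endpoints will be performed using the mITT population with worst case scenario imputation for missing data".

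**Unknown status elsewhere.** For the primary endpoint, Section 4.7.1 has subjects "categorized as cure or failure for the mITT analyses, and as cure, failure or non-evaluable for the PP analysis". For time to resolution of symptoms, Section 4.7.2 censors where symptoms never resolved or "the patient was an early withdrawal and status is unknown".

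**Missed visits.** Sections 1.2 and 3.3 both provide for a subject who misses Visit 2 and comes to Visit 3. Section 3.2 ends participation at Visit 2 for subjects who need additional treatment, and Section 4.3 keeps them in PP if they otherwise qualify.

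**The concern.** Scoring a missing result as failure has a clear meaning for a cure rate at one visit. A category built from two visits describes a change between them. If one of the two statuses is imputed, the table can report a change that nobody observed.

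Late Cure and Recurrence are reported in these two tables. A reader would take a Late Cure as a subject examined and found not cured, then examined later and found cured. Under the plan, some may be subjects who simply missed Visit 2. The number of Recurrences may also depend on which of two sentences the programmer follows, so the same data could yield different tables.

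**Working it through.** **Step 1. Apply the rules to each missing-visit pattern.**

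| Visit 2 | Visit 3 | Category if missing = failure | Categories compatible with what was observed |
|---|---|---|---|
| missing | cure | Late Cure | Persistent Cure or Late Cure |
| cure | missing | Recurrence | Persistent Cure or Recurrence |
| missing | failure | Persistent Infection | Persistent Infection or Recurrence |
| failure | missing | Persistent Infection | Persistent Infection or Late Cure |

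**Step 2. Which rule reaches whom.**

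- *Row 1* follows from Section 4.6 alone. With no Visit 2 data she is non-evaluable, hence outside PP, hence imputed as a failure in mITT.
- *Row 2* depends on scope. PP membership (Section 4.2) requires only the data for the primary endpoint, which is assessed at Visit 2. A Visit 2 cure who misses only Visit 3 can therefore be in PP, and 4.6 does not impute for her. The sentence in 4.7.2 would, if it covers this summary. That sentence governs the secondary endpoints, which 4.7.2 says are listed in 4.3. The four-way summary is not named there and is introduced as an addition. The text does not settle the question.
- *PP subjects without Visit 3* have no stated category in Table 14.2.21.2. They include, by design, Visit 2 failures who leave the study for additional treatment.

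**Step 3. Inputs for size.** Section 4.5 gives planned cure rates c and PP sizes n per arm: BV 0.50 and 0.20, n = 58; VVC 0.70 and 0.20, n = 50; Mixed 0.35 for Combo Gel and 0.10 for each single gel, n = 63. The plan's total reproduces: 2×58 + 2×50 + 3×63 = 405. Exact two-sided Fisher power is 90.6%, 99.94% and 90.6% (per comparison), against the stated 90.0%, above 99.9% and 90%. No stated figure is in dispute.

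The missed-visit rates are assumptions, taken as equal across arms.

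**Step 4. False Late Cures.** Let k be the share of mITT who miss Visit 2 but attend Visit 3, from 0.02 to 0.10. These subjects are outside PP. With this as the only reason for leaving PP, mITT size is N = n/(1−k). With the Visit 3 cure rate equal to c and all of those cured already cured at Visit 2, the count is N × k × c.

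- BV Gel, k = 0.02: 58/0.98 = 59.2, and 59.2 × 0.02 × 0.50 = 0.59.
- BV Gel, k = 0.10: 58/0.90 = 64.4, and 64.4 × 0.10 × 0.50 = 3.22.

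**Step 5. False Recurrences on the wider reading.** Let m be the share of Visit 2 cures who miss Visit 3, from 0.05 to 0.20, all still cured. Among the planned PP subjects the count is n × c × m.

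- BV Gel: 58 × 0.50 = 29.0 cures; 29.0 × 0.05 = 1.45 and 29.0 × 0.20 = 5.80.
- Placebo: 58 × 0.20 = 11.6 cures; 11.6 × 0.05 = 0.58 and 11.6 × 0.20 = 2.32.
- Under 4.6 alone the count among these PP subjects is 0.

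| Study (higher vs lower cure-rate arm) | False Late Cures per arm | False Recurrences per arm, 4.7.2 reading |
|---|---|---|
| BV Gel vs Placebo | 0.59-3.22 vs 0.24-1.29 | 1.45-5.80 vs 0.58-2.32 |
| VVC Gel vs Placebo | 0.71-3.89 vs 0.20-1.11 | 1.75-7.00 vs 0.50-2.00 |
| Combo Gel vs each single gel | 0.45-2.45 vs 0.13-0.70 | 1.10-4.41 vs 0.32-1.26 |

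The counts scale with the cure rate, so equal missingness produces unequal numbers of artefacts. As a share of Visit 2 cures, false Recurrence is m in every arm.

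**The case against.** **The imputation is still worst case.** A reader might infer that failure imputation is simply not conservative here. The documents do not support that. In rows 1 and 2 of the pattern table, the assigned category is the worse of the two that fit the observed visit. Persistent Cure is understated, and false Recurrences fall mainly on the arm with more cures. This objection stands: the fault is the wrong label. Late Cure read on its own is the one cell that can look favourable.

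**Recurrence is conditional.** A reader might also take the Recurrence problem as certain, or see a contradiction between 4.6 and 4.7.2. Neither follows. The narrow reading is tenable, and under it no PP subject is imputed. What remains is an unstated scope.

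**The table formats are elsewhere.** Section 1 places them in a companion document that is not at hand and may already carry a missing or non-evaluable row. That is a fair limit: this point concerns the SAP text.

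**There is a merit in the present rule.** Counting a missed Visit 2 as no cure keeps the Visit 2 margin of the mITT table equal to the primary result. Test-of-cure results are also listed by subject (Listing 16.2.6), so observed status can be traced. Both are true, but neither makes an unobserved transition a proper entry under Late Cure.

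**Conclusion.** The point holds as a minor misclassification. The Late Cure path follows from 4.6, 4.7.2 and the missed-visit provision in Sections 1.2 and 3.3. The Recurrence path holds for PP members only if the sentence in 4.7.2 covers this summary; outside PP, 4.6 already produces it. PP subjects without Visit 3 have no stated category.

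Under the assumed rates the effect is a few subjects per arm. The figures should not be read as upper bounds. They use the point cure rates, and the upper ends of the ranges in Section 4.5 give more: at m = 0.20, false Recurrences become 58 × 0.55 × 0.20 = 6.4 on BV Gel, 50 × 0.75 × 0.20 = 7.5 on VVC Gel and 63 × 0.40 × 0.20 = 5.0 on Combo Gel. They also leave out other reasons for being in mITT but not PP, such as major violations and self-medication. In the other direction, they assume that every affected subject was in truth cured at both visits.

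The tables are descriptive with no planned test. The primary analysis is unaffected, and no arm bias is claimed for recurrence as a share of Visit 2 cures.

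**What to change.** In Section 4.6 or 4.7.2, state that Late Cure, Recurrence and Persistent Cure are assigned only when cure status at both visits is observed, or is failure by a stated rule (additional treatment or self-medication).

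In Tables 14.2.21.1 and 14.2.21.2, show three further rows by arm, unless the companion formats already have them:

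- Visit 2 missing
- Cure at Visit 2, Visit 3 missing
- Failure at Visit 2, no Visit 3 (including subjects terminated for additional treatment)

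The last group may be counted as Persistent Infection if the SAP says so. State also that worst-case imputation does not apply to this summary, or show the imputed version beside the observed one.

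The cost is one or two sentences and up to three rows in two descriptive tables, with no new data. There are two drawbacks. An observed-only table can miss relapses in subjects who did not return, which is a reason to keep the imputed version beside it. Its Visit 2 margin also no longer matches the imputed primary result unless the missing rows are counted in.

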4.3 Efficacy Endpoints and Evaluations

The primary and secondary endpoints are reflective of each of the infection studies within the protocol. These include:

Primary Endpoints

- BV Study: BV cure rate, with cure defined as normal/physiologic discharge, negative whiff test, and < 20% clue cells (i.e. clinical cure)
- VVC Study: VVC cure rate, with cure defined as resolution of all signs and symptoms attributable to VVC (i.e. clinical cure)
- Mixed Infection Study: Mixed Infection cure rate, with cure defined as BV cure (i.e. BV clinical cure) AND a VVC cure (i.e. VVC clinical cure)

Primary efficacy endpoint evaluations will occur at the test-of-cure Visit 2.

If a subject requires additional treatment for vaginal discomfort/symptoms (i.e. a BV subject requiring treatment for BV, a VVC subject requiring treatment for VVC or a Mixed Infection subject requiring treatment for BV and/or VVC) prior to or at Visit 2, the subject will be considered a treatment failure. These subjects will be evaluable for the modified intent-to-treat (mITT) and the per-protocol (PP) population analyses, providing all other evaluability criteria for these population groups have been met.

Additionally, if a subject self-medicates herself for vaginal discomfort/symptoms at any time prior to Visit 2, the subject will be considered a treatment failure. If this occurs, the subject will remain evaluable for the mITT analyses but will be non-evaluable for the PP analysis.

Secondary Endpoints

Note, for BV a Gram stain Nugent score cure will be defined as a score of < 4, i.e. 0 – 3.

- BV Study: BV clinical and Gram stain Nugent score combined cure rate, and Gram stain Nugent score cure rate alone; changes/improvements in Amsel criteria and Nugent scores; time to resolution of symptoms
 - In addition, cure rates over time will be explored
- VVC Study: VVC clinical and mycologic cure rates combined and mycologic cure alone; changes/improvements in signs and symptoms scores; eradication (or persistence) of individual fungal species; time to resolution of symptoms
- Mixed Infection Study: BV clinical and Gram stain Nugent score cure rates alone and combined; changes/improvements in Amsel criteria and Nugent scores; VVC clinical and mycologic cure rates alone and combined; changes/improvements in signs and symptoms scores; eradication or persistence of individual fungal species; time to resolution of symptoms

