14.2 Efficacy Summaries

Table 14.2.1.1	Summary of Primary Endpoint for BV Study – Test-of-Cure, mITT Population
Table 14.2.1.2	Summary of Primary Endpoint for BV Study – Test-of-Cure, PP Population
Table 14.2.2.1	Summary of Primary Endpoint for VVC Study – Test-of-Cure, mITT Population
Table 14.2.2.2	Summary of Primary Endpoint for VVC Study – Test-of-Cure, PP Population
Table 14.2.3.1	Summary of Primary Endpoint for Mixed Infection Study – Test-of-Cure, mITT Population
Table 14.2.3.2	Summary of Primary Endpoint for Mixed Infection Study – Test-of-Cure, PP Population
Table 14.2.4	Exploratory Analysis of Primary Endpoint by Month of Study, For Patients Receiving BV Gel – Test-of-Cure, mITT Population
Figure 14.2.5	Time Plot of Primary Endpoint by Month of Study, For Patients Receiving BV Gel – Test-of-Cure, mITT Population
Table 14.2.6	Summary of Visit 2 Symptom and Sign Severity Score, mITT Population
Table 14.2.7	Summary of Visit 2 Pelvic Exam, mITT Population
Table 14.2.8	Summary of Visit 2 Compliance Assessment, mITT Population
Table 14.2.9	Summary of Visit 2 Need for Additional Treatment, mITT Population
Table 14.2.10.1	Summary of Visit 2 BV Clinical Cure, mITT Population
Table 14.2.10.2	Summary of Visit 2 BV Clinical Cure, PP Population
Table 14.2.11.1	Summary of Visit 2 VVC Clinical Cure, mITT Population
Table 14.2.11.2	Summary of Visit 2 VVC Clinical Cure, PP Population
Table 14.2.12.1	Summary of Visit 2 Gram Stain Cure, mITT Population
Table 14.2.12.2	Summary of Visit 2 Gram Stain Cure, PP Population
Table 14.2.13.1	Summary of Visit 2 Candida Culture Cure, mITT Population
Table 14.2.13.2	Summary of Visit 2 Candida Culture Cure, PP Population
Table 14.2.14.1	Summary of Visit 2 Combined BV Clinical and Gram Stain Cure, mITT Population
Table 14.2.14.2	Summary of Visit 2 Combined BV Clinical and Gram Stain Cure, PP Population
Table 14.2.15.1	Summary of Visit 2 VVC Clinical and Candida Culture Cure, mITT Population
Table 14.2.15.2	Summary of Visit 2 VVC Clinical and Candida Culture Cure, PP Population

Table 14.2.16	Summary of Visit 2 Change in Pelvic Exam Results, mITT Population
Table 14.2.17	Summary of Visit 2 Change in Signs and Symptoms, mITT Population
Table 14.2.18	Summary of Visit 2 Eradication/Persistence of Candida Species, mITT Population
Table 14.2.19	Summary of Time to Resolution of Symptoms, mITT Population
Figure 14.2.20	Kaplan-Meier Curve of Time to Resolution of Symptoms

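### The by-month look at BV Gel potency shows BV Gel alone and, read literally, scores the Mixed Infection arm on a cure that also needs VVC to resolve (low severity)

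*SAP*

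**What the plan says.** The last paragraph of SAP section 4.7.2 gives the purpose, which concerns BV Gel as the trial went on: "A descriptive analysis of the primary endpoint (cure rate) for BV subjects will be performed to assess the impact of loss of potency". Cure proportions are computed "among cohorts of patients completing Visit 2 during each month the study was underway", and the arms are fixed by the next sentence: "These proportions will be tabulated by month for the BV Gel arms of the BV study and the mixed infection study". A plot by month accompanies the table.

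The outputs in section 14.2 match. Table 14.2.4 is titled "Exploratory Analysis of Primary Endpoint by Month of Study, For Patients Receiving BV Gel" and Figure 14.2.5 "Time Plot of Primary Endpoint by Month of Study, For Patients Receiving BV Gel". Both carry the mITT label.

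Section 4.3 defines the primary endpoint separately for each study. In the BV Study it is BV clinical cure. In the Mixed Infection Study it is "Mixed Infection cure rate, with cure defined as BV cure (i.e. BV clinical cure) AND a VVC cure". BV clinical cure alone is a secondary endpoint of the Mixed Infection Study. Section 14.2 also gives BV clinical cure its own output, Table 14.2.10.1: "Summary of Visit 2 BV Clinical Cure, mITT Population".

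Section 1.2 randomises Placebo Gel 1:1 against BV Gel in the BV Study, and BV Gel, VVC Gel and Combo Gel 1:1:1 in the Mixed Infection Study. Placebo Gel and VVC Gel contain no metronidazole.

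**The concern.** There are two weaknesses, both measured against the display's own purpose.

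- **No concurrent arm.** If BV Gel cure falls from month to month, the gel may have weakened, or the subjects, sites or season may have changed. A table of BV Gel alone looks the same either way. A flat BV Gel curve is equally hard to read. Randomised arms that share the calendar drift but not the metronidazole are available and are left out.

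- **The cure applied to the Mixed Infection arm.** The paragraph and both titles say primary endpoint, which under section 4.3 means BV and VVC cure together. The same paragraph refers to BV subjects, and section 4.3 lists cure over time under the BV Study only; both point to BV cure. Two programmers could build different tables. The literal reading is the worse one, because a potency signal for metronidazole would be filtered through the resolution of candidiasis in subjects given no antifungal.

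What is at stake is how well an exploratory table can be read, not the trial's efficacy conclusions.

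**Working it through.** **Inputs.** From SAP section 4.5: BV Study, BV Gel .50 (.45–.55), Placebo Gel .20 (.15–.25), 58 per arm. VVC Study, VVC Gel .70, Placebo Gel .20. Mixed Infection Study, BV Gel .10 (.05–.15), VVC Gel .10, Combo Gel .35, 63 per arm. The display itself states no figure.

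**1. The plan's own figures.** Power of the two-sided Fisher's exact test at 0.05, by full enumeration, is 90.6% for .50 v .20 with 58 per arm and 90.6% for .35 v .10 with 63 per arm. The plan states 90.0% and 90%. The planning rates and sizes are therefore coherent and can be used below.

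**2. What BV Gel alone can show.** Let BV Gel cure in the BV Study fall from 55% to 45%, with Placebo at 25% at the start. Table 14.2.4 is identical in all four cases:

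| Cause | Later Placebo rate | Later difference |
|---|---|---|
| Potency loss only | 25% | 45 − 25 = 20 points |
| Drift, same ratio | 25 × 45/55 = 20.5% | 24.5 points |
| Drift, same odds ratio | odds 0.3333 × 0.669 = 0.2231, so 18.2% | 26.8 points |
| Drift, same points | 15% | 45 − 15 = 30 points |

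The starting difference is 30 points. Only the Placebo column distinguishes the rows.

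**3. Which cure.** Planned Mixed cure on BV Gel is 63 × .10 = 6.3 subjects (3.2 to 9.5 over .05–.15). The SAP gives no BV cure rate for this arm. I assume .50, as in the BV Study. This fits the plan's rates if the two cures are independent: .50 × .20 = .10 on BV Gel and .50 × .70 = .35 on Combo Gel. On the same assumption, a fall in BV cure from .55 to .45 becomes a fall in Mixed cure from .55 × .20 = .11 to .45 × .20 = .09.

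- In halves of 31.5 subjects, Mixed cures go from 3.5 to 2.8, while BV cures go from 17.3 to 14.2.
- For a 30% relative fall on both scales, z = (.50 − .35)/√((.25 + .2275)/31.5) = 1.22 on BV cure. On Mixed cure, z = (.10 − .07)/√((.09 + .0651)/31.5) = 0.43.

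Neither is a clear signal, but Mixed cure carries much less information.

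**4. Month by month.** Accrual length is not stated. Assuming 6 to 12 months of even accrual, each BV Gel arm has about 10 to 5 subjects per month (58/6 = 9.7, 58/12 = 4.8).

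- BV Study: 5 of 10 cures has an exact 95% interval of 19% to 81%; 2 of 5 has 5% to 85%.
- Mixed arm on Mixed cure: 6.3/6 = 1.05 to 6.3/12 = 0.53 cures per month. The chance of none in a month is .9^10 = 35% to .9^5 = 59%.
- Mixed arm on BV cure at .50: the chance of none is .5^10 = 0.1% to .5^5 = 3%.

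**5. What the added arm can and cannot do.** With two periods of 29 per arm in the BV Study, the 95% half-width is:

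- change in difference: 1.96 × √(2 × (.25 + .16)/29) = 33 points;
- change in Placebo alone, 25% to 15%: 1.96 × √((.1875 + .1275)/29) = 20 points.

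In step 2 potency loss and drift end 4.5 to 10 points apart, so the comparator gives context and does not discriminate between them.

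**The case against.** The strongest reply is that the analysis is labelled descriptive and exploratory and that no decision rests on it. Showing only the product in question is then a choice, not an error. By the numbers above, the comparator cannot separate the scenarios, and calendar month remains only a proxy for product age. Subject-level listings of kit number and test-of-cure (16.1.15 and 16.2.6) are planned for all arms. A default reading of the endpoint also exists: section 4.7.1 refers to section 4.3 for each study's cure definition, so primary endpoint can be read as Mixed cure. The companion format document named in section 1 may settle the matter.

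Much of this stands. It caps the severity, and it removes any case for a formal contrast of differences between wide periods. It does not remove the point. A concurrent arm improves the reading of the display at almost no cost. The default reading of the endpoint is also the one least suited to the stated purpose.

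A reader might also infer that cohorts of subjects completing Visit 2 contradict the mITT label, since section 4.7.2 says: "The analysis of the secondary endpoints will be performed using the mITT population with worst case scenario imputation for missing data". The SAP does not support that. Grouping by month of Visit 2 needs a Visit 2 date, so the table can be read as mITT subjects who attended, with imputation still applying to incomplete Visit 2 data. Nothing in the SAP claims that the monthly rates reconcile with Table 14.2.1.1.

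**Conclusion.** The point holds at low severity. As written, the display cannot set a BV Gel trend against concurrent drift. On the literal reading it also scores the Mixed Infection arm on an outcome near the floor (10%, about 6 of 63) that depends on VVC resolving without terconazole.

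It would be too strong to infer that the primary analyses are affected, or that adding a comparator would establish or rule out potency loss. No test, alpha or sample size is tied to the display, and the precision in step 5 is far too low.

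The two structural observations rest on the SAP text alone. The sizes rest on assumptions: 6 to 12 months of even accrual, BV cure of 50% on BV Gel in the Mixed Infection Study, independence of the two cures, and the evaluable (per-protocol) sample sizes, whereas the display is labelled mITT.

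**What to change.** In the last paragraph of section 4.7.2, Table 14.2.4 and Figure 14.2.5:

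- Name BV clinical cure at Visit 2 as the endpoint in both studies, and reword the two titles to match.
- Separately by study, show the concurrent metronidazole-free arm beside BV Gel: Placebo Gel in the BV Study, VVC Gel in the Mixed Infection Study. Keep this descriptive, with no test.
- Add one sentence saying that monthly rates are imprecise and that the display describes but does not prove or exclude potency loss.
- Optionally, label the outputs as mITT subjects with a Visit 2, or group by month of randomisation.

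The cost is one revised paragraph and a slightly larger table and figure. The data are already collected, and BV clinical cure is already derived for Tables 14.2.10.1 and 14.2.10.2.
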